5.2. Participant Numbering

Prior to enrollment, participants that sign an ICF will be assigned a 3-digit screening number, assigned sequentially, starting at 001 (through 099). Participants who meet the protocol's eligibility criteria and are scheduled for a Study Day 1 visit will be assigned a 5-digit participant number. The first two digits will be "01" and will identify the study site and be linked to the next three-digit number also will be assigned sequentially starting with 101.

- For example, the first three potential participants that are screened would be assigned: 001, 002 and 003. If the second and third participants qualify for the trial and are scheduled for a Study Day 1 visit, they will be assigned 01-101 and 01-102, respectively. If two additional individuals are screened, they would be assigned screening numbers of 004 and 005. If only 005 is found to be eligible and scheduled for Study Day 1, that participant will be assigned 01-103.

5.3. Withdrawal of Participants

Participants can withdraw their consent to continue participating in this trial at any time, without prejudice and with no impact on their subsequent medical care.

The Investigator can withdraw a participant from continued participation in the trial if, in his or her clinical judgment, it is in the best interest of the participant or if the participant cannot

CONFIDENTIAL

comply with the experimental procedures and related visits that are critical to assess the safety of the investigational product.

Regardless of the reason, any withdrawal (or discussion about withdrawing) from continued participation in the trial will be recorded in the participant's personal medical record (i.e., source document). If a patient prematurely discontinues participation in the trial, the date of and reason(s) for discontinuation will be recorded in the electronic case report form (eCRF).

Among the reasons that may require participants to prematurely discontinue participation is that they may not be able to comply with one or more eligibility criteria such as the prohibited use of certain concomitant medications. If the Investigator withdraws a participant from the trial, the reason(s) for the decision will be explained to the participant. If the Investigator feels it is needed, the participant may be referred for continued PTSD (and/or other medically necessary) care.

As necessary, participants that are withdrawn due to AEs will continue to be clinically monitored until the event resolves, unless the participant refuses to do so.

Whenever possible, the Investigator or another member of the research study team will ask any participant that chooses to withdraw or is withdrawn by the Investigator to return to the study site as soon as convenient to undergo the protocol's mandated tests, examinations, procedures and assessments that are required for the Day 30, EoT visit. Nonetheless, the decision to return to the study site and undergo some or all of the activities required at the EoT visit rests entirely with the participant. As noted in Section 5.2, the patient should not be coerced into continuing to be involved in the trial, even in a less demanding manner.

6. STUDY DRUGS

6.1. Product Description

The product is a whole dried organic hallucinogenic mushroom (RTT1121 also called JMF-01), which has been milled and then subsequently formulated into a solid chocolate dosage form (drug product) prior to administration to patients. The total dose is standardized to 30 mg (\pm 10%) of psilocybin, delivered as three individual units of chocolate. Each chocolate corresponds to 10 mg of psilocybin.

- The whole organic psilocybin mushrooms are obtained from a Drug Enforcement Administration (DEA)-approved supplier. The composition of the mushrooms is verified by a qualified laboratory.

6.2. Packaging and Labeling

Organic whole dried ground psilocybin mushrooms will be placed in a plastic container labelled with the investigational product dosage of 10 mg of psilocybin, (psilocybin is approximately 1% of the total mushroom weight), batch number, participant number, and date of use. DEA Schedule C-I Drug labels will indicate the manufacturer, expiration date, study identification, and that study drug is only to be administered in the presence of study investigators.

6.3. Product Storage and Handling

Psilocybin-containing mushrooms are a Schedule 1 controlled substance and will be stored and

CONFIDENTIAL

handled in compliance with relevant institutional policies, federal and state regulations, and in accordance with DEA requirements.

Psilocybin mushrooms may be stored at room temperature (68-77 °F).

6.4. Product Stability

Information on the concentrations of psilocybin and other active metabolites and the stability of these compounds will be provided by a certified testing laboratory.

6.5. Dose and Administration

6.5.1 Dose

For the visit, study participants will self-administer a total dose of 30 mg ($\pm 10\%$) of psilocybin, derived from whole, dried, ground organic psilocybin mushrooms (RTT1121 also called JMF-01), which has been milled and formulated into 3 solid units of chocolate. Each chocolate contains to 10 mg of psilocybin and all three units of chocolate will be consumed concurrently during a single dosing session.

6.5.2 Route of Administration & Fasting State Prior to Dosing

Whole, dried, ground, organic psilocybin mushrooms are intended to be taken orally as a chocolate preparation. Participants will self-administer the psilocybin mushrooms on Study Day, 1 in a fasting state, following completion of the protocol's required pre-dose tests, examinations and assessments.

6.6. Product Supply and Accountability

The Investigator (or qualified designee), under the direction of a Schedule I license holder, will supply participants with whole organic psilocybin mushrooms for self-administration. All psilocybin mushrooms dispensed during the study will be tracked by date dispensed, dose, batch, and participant number.

Drug Dispensation and Disposition Forms will be provided to the study site to track drug supply and accountability throughout the study. Records pertaining to the use of Schedule I compounds will be maintained in accordance with relevant federal and state Regulations, and institutional policies, where applicable.

6.7. Allowed and Prohibited Medications and Therapies

6.7.1 Prohibited Medications/Treatments

The consumption of synthetic psilocybin or psilocybin mushrooms (other than the single dose of the whole organic mushroom study drug) as well as LSD, DMT, ayahuasca, peyote, mescaline, and ketamine are forbidden during the study (and for at least 30 days prior to Study Day 1).

Medications with the potential for adverse drug-drug interactions including centrally acting serotonergic agents also are forbidden during the study.

Participants must agree not to participate in any other interventional clinical trials and/or additional treatments during this study.

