5.1.1 Inclusion Criteria

1. Individuals ≥ 18 years of age
2. Have a diagnosis of Post-Traumatic Stress Disorder (PTSD) as defined:
 - Meet Diagnostic and Statistical Manual-5th edition (DSM-5) criteria for current PTSD with a duration of 6 months or longer as assessed by a study psychiatrist.
 - Determination of at least one traumatic event as determined by the LEC-5
 - A score of at least 33 on the PCL-5
3. Willing and able to provide signed informed consent which includes compliance with the requirements and restrictions listed in the informed consent form (ICF) and in this protocol.
 - Willingly agreed to provide verbal consent to provide needed pre-screening information, including medical history, concomitant medications, etc., prior to signing the ICF.
4. Be willing to commit to self-administering the study drug, to completing the QoL and PRO instruments, and attending all study visits.
5. Participants must be able to evaluate their average pain on the BPI (Brief Pain Inventory) over the past week.
6. Acceptable renal functioning as determined by no significant prior medical history and results of clinical laboratory evaluations done at Screening and on Day 1 (e.g., eGFR >45 (mL/min/1.73 m²))

7. Acceptable hepatic functioning as determined by no significant prior medical history and results of clinical laboratory evaluations done at Screening and on Day 1 (e.g., liver enzymes ≤ 1.5 x the upper limit of normal, 'ULN')
8. Agree to only use the psilocybin mushroom provided by site staff and not use any other psilocybin (or similar drug) in any form for at least 30 days prior to Study Day 1 and for 30 days following the single-dose study drug treatment.
9. Is willing to wear, sync daily, and charge twice weekly a provisioned health tracking wearable device every day during sleep and daily activity. If the participant already has the same, or compatible device, they can use their own.
10. Agree to not use any psychoactive drugs, partake alcoholic beverages, self-administer ondansetron (or other selective serotonin reuptake inhibitors 'SSRIs', serotonin-norepinephrine reuptake inhibitors, 'SNRIs' and monoamine oxidase inhibitors, 'MAOs'), cannabis, and/or any other non-routine PRN medications within 24 hours of Study Day 1. Exceptions include daily use of caffeine, nicotine, and opioid pain medication

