11. Be stable on any pre-study medications and/or psychotherapy regimen prior to study entry. Agree to inform physician(s)/clinician(s) providing current care about your participation in the study (or permit the research site study staff to do so). Agree to report any changes in medication or psychotherapy treatment regimen during the study, to study staff.
12. If female and of childbearing potential, the participant is eligible for the trial only with a negative urine pregnancy test during Screening and on Study Day 1. [If a result is uncertain (e.g., potential false positive), a serum human chorionic gonadotropin (hHCG) test may be performed prior to the administration of the study drug.] Fertile females agree to use a highly effective form of birth control during the 30-day posttreatment period and must confirm that they have no intent to try to become pregnant or any need to breastfeed during this period.
 - Adequate birth control methods include intrauterine device (IUD), injected or implanted hormonal methods, oral hormones plus a barrier contraception, or double barrier contraception. Two forms of contraception are required with any barrier method or oral hormones (i.e., condom and diaphragm, condom or diaphragm and spermicide, oral hormonal contraceptives and spermicide or condom). Not of childbearing potential is defined as permanent sterilization or postmenopausal females.
13. Be proficient in reading and writing in English and able to effectively communicate with site staff.
14. Agree not to participate in any other interventional clinical trials during the study.

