5.1.2 Exclusion Criteria

1. Currently uncontrolled hypertension. ($>140/90$ at Screening and $>145/95$ on Study Day 1).
2. History of recent seizure (within 3 months of Study Day 1).
3. History of stroke or transient ischemic attacks.
4. Preexisting history of valvulopathy or pulmonary hypertension.
5. A marked prolongation of QT interval (i.e., $QT \geq 450$ msec) over a series of 3 ECGs performed within 5-6 minutes.

CONFIDENTIAL

6. Currently uncontrolled diabetes ($HbA1c > 8.0\%$).
7. Potential for adverse drug-drug interactions such as the use of centrally-acting serotonergic agents within 24 hours prior to and for 72 hours following study drug administration on Study Day 1.
8. Significant suicide risk defined by (1) suicidal ideation as endorsed on items 4 or 5 on the Columbia Suicidal Severity Rating Scale (C-SSRS) within the last 6 months, at Screening, or at Baseline (Visit 1), or; (2) suicidal behaviors within the last 12 months as assessed by C-SSRS.
9. Patients with severe anxiety and depression measured as following: Participants with scores of 15 & above on Generalized Anxiety Disorder-7 (GAD-7) scale, and/or with scores of 20 & above on Patient Health Questionnaire-9 (PHQ -9).
10. Are pregnant or nursing or are women of childbearing potential who are not practicing a highly effective means of birth control.
11. Have any allergies or contraindication to psilocybin mushrooms.
12. Current users of psilocybin, LSD, DMT, Ayahuasca, Peyote, mescaline, and ketamine over the past 30 days will not qualify for the study unless the use of these agents is stopped for 30 days prior to Study Day 1 and the participant agrees to not use these (or similar) agents for 30 days after Study Day 1.
13. Are not able to attend face-to-face visits at the study site or plan to move out of the area prior to the 3-month LTFU visit.
14. Have any current problem that, in the opinion of the Investigator or Medical Monitor, might interfere with an individual's participation in the study or confound the assessment of safety and/or efficacy of the study drug.

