6.7.2 Permitted Psychotherapy

Participants will undergo regular psychotherapy.

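### The restriction on centrally acting serotonergic agents has two incompatible durations: 96 hours around dosing in exclusion 7, and the whole study in Section 6.7.1

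*Protocol*

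**What the plan says.** Four operative passages in the current Protocol bear on this restriction.

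- **Section 5.1.2, exclusion 7** (exclusion 8 in the synopsis) gives as its example of a potential drug interaction "the use of centrally-acting serotonergic agents within 24 hours prior to and for 72 hours following study drug administration on Study Day 1".
- **Section 6.7.1** says: "Medications with the potential for adverse drug-drug interactions including centrally acting serotonergic agents also are forbidden during the study". It gives no end date.
- **Section 5.1.1, inclusion 10** (same in the synopsis) has the participant agree not to take SSRIs, SNRIs, MAO inhibitors and several other items, in a list that closes with "any other non-routine PRN medications within 24 hours of Study Day 1".
- **Section 5.1.1, inclusion 11** requires the participant to "Be stable on any pre-study medications and/or psychotherapy regimen prior to study entry" and to report later changes. It makes no exception for serotonergic agents.

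Section 5.3 lists failure to comply with eligibility criteria, with prohibited concomitant medication as the example, among the reasons that may require discontinuation. Section 8.4 collects all medications, with start and stop dates, from Screening to the 3-month visit.

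On psychotherapy, Section 6.7.1 also says "Participants must agree not to participate in any other interventional clinical trials and/or additional treatments during this study", while Section 6.7.2 says "Participants will undergo regular psychotherapy".

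**The concern.** The restriction is there because of possible drug interactions, and safety is the trial's primary objective. Staff need one rule to tell a participant when such an agent must be stopped and whether it may be restarted. As written, the answer depends on which section they open.

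Three things are at stake. The first is conduct: whether a participant who restarts is recorded as a protocol deviation, or even discontinued, could depend on who makes the decision. The second is the primary endpoint. It includes mental and psychotic adverse events, Section 10 has the investigator weigh the product against other causes, and under Section 9.4 one severe event judged possibly related pauses the study. Whether a participant is on or off a serotonergic agent is one of the facts that judgement uses. The third is the exploratory ratings, which are compared with baseline without a control group.

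**Working it through.** No design figure depends on this point. The check sets the passages side by side and counts days.

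**Inputs**
- Exclusion 7: 24 h before dosing and 72 h after.
- Section 6.7.1: during the study.
- Section 4.3: individual participation of 3.5 to 4.0 months. The last visit is about 90 days after Day 1.
- Assumption: 30 days per month.

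**Length of each window**
- Exclusion 7: 24 + 72 = 96 h = 4 days.
- Section 6.7.1, counted from dosing: about 90 days.
- Section 6.7.1, counted from Screening: 3.5 × 30 = 105 days to 4.0 × 30 = 120 days.

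**Ratio of Section 6.7.1 to exclusion 7**
- 90 / 4 = 22.5
- 105 / 4 = 26.3
- 120 / 4 = 30

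**A test case.** A participant restarts a serotonergic agent on Day 5, which is 96 h after dosing.

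| Passage | Status on Day 5 |
|---|---|
| Exclusion 7 | Outside the 72 h limit, so compliant |
| Inclusion 10 | Compliant if its 24 h are read as pre-dose |
| Inclusion 11 | The change must be reported; it is not barred |
| Section 6.7.1 | Breach |

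**Which ratings are exposed.** GAD-7 and PHQ-9 have six post-dose ratings: Day 1 at 8 h, then Days 2, 4, 8, 30 and 90. Under exclusion 7, Day 4 lies at the 72 h boundary and Days 8, 30 and 90 (3 of 6) fall after the restriction has ended. Under Section 6.7.1 none of the six does.

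**Inclusion 10 and 11.** Inclusion 10 does not say whether its 24 hours run before Day 1, after it, or both. Read as pre-dose, it nests inside exclusion 7 and adds no further conflict. Inclusion 11 sits awkwardly with the rest: a stable serotonergic regimen satisfies it, must be interrupted under exclusion 7, and could not be taken at all during the study under Section 6.7.1.

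**Placement.** The 72 h post-dose part of exclusion 7 is a condition on future conduct. It cannot be assessed when eligibility is decided.

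**The case against.** The best defence is that exclusion 7 governs entry and Section 6.7.1 governs conduct. Exclusion 7 introduces its window as an example and never grants permission to resume, and anyone who obeys Section 6.7.1 after dosing also meets the 72 h limit. That is fair as far as it goes, but it leaves the 72 h limit with no function and does not tell staff that the longer rule prevails.

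Several stronger readings are tempting, and the documents do not support them.

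- **Three conflicting windows and a 100-fold range.** This sets the 1-day reading of inclusion 10 against the whole study. Inclusion 10 is ambiguous and nests in exclusion 7 if read as pre-dose, so the real comparison is 4 days against 90 to 120.
- **A direct contradiction with inclusion 11.** Section 5.1 requires every inclusion criterion and no exclusion criterion to be met, so stability alone admits nobody. The tension is implied by the lack of an exception.
- **Inconsistency between sites.** There is one site. The risk lies between staff or participants there.
- **Withdrawal on Day 5.** Section 5.3 says prohibited medication may require discontinuation, ties this to eligibility criteria and does not cite Section 6.7.1. It is a possible consequence, not a certain one.
- **The same conflict for psychotherapy.** Section 6.7.2 is headed as permitted psychotherapy, and a specific permission answers a general phrase in a sentence about other trials. The wording is loose, no more.
- **Medication review that stops at Day 1 in Table 1.** The row may have been disturbed when the table was extracted, and Sections 7.1.5 to 7.1.9 and 8.4 require medication review or collection at the later visits.
- **Ratings at Days 2 to 4 spoiled by interrupted medication.** Both rules keep the participant off the agent up to the 72 h boundary, so reconciling them would not remove that effect.

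**Conclusion.** The concern holds in a limited form. Exclusion 7 and Section 6.7.1 give the same restriction durations of 96 hours and about 90 to 120 days, a ratio of roughly 22 to 30 depending on whether Screening counts as part of the study. Both are operative current text, and a participant can satisfy one while breaching the other. Because this is a drug-interaction restriction in a trial whose primary objective is safety, it needs correcting before it is applied.

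A reader might infer that the later ratings will mix participants on and off medication, so that change from baseline cannot be interpreted. The Protocol does not establish that. Mixing would occur only if the shorter window were applied to some participants and they resumed. The ratings are exploratory, attribution is already limited in a single-arm open-label study, and medication status can be handled in a SAP that is not at hand. What a SAP cannot do is decide what participants are told to take.

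The finding rests on the wording alone and assumes 30-day months. It does not say which duration is clinically right.

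**What to change.** Amend inclusion 10 and 11, exclusion 7 (and the matching synopsis items) and Section 6.7.1 so that they carry one statement of:

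1. which agents are restricted;
2. from when to when, relative to dosing;
3. whether resumption is allowed;
4. how that fits with a stable pre-study regimen.

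The clinical choice is the sponsor's. Keep what must be true before dosing in the entry criteria, and move the post-dose restriction to Section 6.7.1 as a rule of conduct. State there, and in Section 5.3, whether a breach is a deviation, a possible ground for discontinuation, or both.

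As a side point, align the phrase on additional treatments in Section 6.7.1 with Section 6.7.2, so that the place of psychotherapy is clear.

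The cost is amendment wording. No new data collection is needed, because the medication dates recorded under Section 8.4 already allow on/off status to be described at each visit.

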6.7.2 Permitted Psychotherapy

Participants will undergo regular psychotherapy.

7. STUDY PROCEDURES AND EVALUATIONS

7.1. Timing of Procedures

Procedures will be conducted according to the Schedule of Events Table 1.

7.1.1 Recruitment of Participants

Participants will be recruited via IRB-approved materials which may include letters of referral sent to psychiatrists and psychotherapists, primary care providers, advertisements or announcements placed in appropriate locations or on appropriate internet sites and websites. Participants also may be made aware of the trial by word of mouth.

Approximately 30 potential participants with PTSD may need to be screened to identify 24 participants that will receive the single dose of study drug. This figure assumes a screen failure rate of approximately 30%. In addition, participants that are treated, but that prematurely discontinue participation in the trial on or before Study Day 3, for any reason except if due to an adverse event, may be replaced at the discretion of the Investigator.

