Title:	An Open-Label, Phase 1 Study of the Safety, Pharmacokinetic Profile, and Preliminary Efficacy, of Organic Whole Psilocybin-Containing Mushrooms in Patients Suffering from PTSD
Brief Title:	Safety and Preliminary Efficacy of Organic Whole Psilocybin-Containing Mushrooms to Treat Patients Suffering from PTSD
Indication:	Post-Traumatic Stress Disorder (PTSD)
Protocol Number:	SRI-HRTT21
Phase:	I
Investigational Product:	Whole Psilocybin-Containing Mushrooms (30 mg \pm10 % of psilocybin) milled and formulated into three solid chocolates, each delivering 10 mg of psilocybin. All three units are administered concurrently during a single dosing session.
Route of Administration	Oral
Sponsor:	Scottsdale Research Institute
Principal Investigator:	[name]
Number of Participants:	24 treated participants
Number of Trial Sites:	1
Study Duration:	The overall duration of the patient enrollment, treatment and follow-up portions of the trial is expected to last 9 months. The duration of each patient's participation that completes the trial is expected to be between 3.5 and 4.0 months, depending on the length of time a patient is in the Screening phase (up to 4 weeks).
Primary Objective:	Primary Endpoints

 To evaluate the safety of psilocybin mushrooms. 	
 Number/Incidence of adverse events (AEs), and serious adverse events (SAEs) graded using the National Cancer Institute (NCI) Common Terminology Criteria for Adverse Events (CTCAE) version 5.0. 
 Number/Incidence of AE's related to clinically significant ECG/cardiac function abnormalities Number/Incidence of AE's related to Heart Rate Tachycardia ($HR > 100bpm$) Bradycardia ($HR < 50 bpm$) Number/Incidence of AE's related to Blood Pressure 
 Hypotension Hypertension Number/Incidence of AE's related to Liver Function 
 Liver function tests (i.e., liver enzymes) Number/Incidence of AE's related to Kidney Function 
 Renal function tests Number/Incidence of Mental and Psychotic AE's

Secondary Objective:
 
 To characterize the pharmacokinetic profile of psilocin, the major active metabolite of psilocybin (using non-compartmental analysis). 	
Secondary Endpoints
 
 AUC₀₋₁₂, AUC_{0-∞} T_{max} C_{max} t_{1/2}

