4.4. Study Endpoints

4.4.1 Primary Endpoints

Primary endpoints will be assessed using descriptive statistics. The statistical approaches are described Section 13.3 and will be detailed in the Statistical Analysis Plan (SAP) that will be developed and finalized before any analyses are undertaken.

- Number/Incidence of adverse events (AEs), and serious adverse events (SAEs) graded using the National Cancer Institute (NCI) Common Terminology Criteria for Adverse Events (CTCAE) version 5.0.
 - Number/Incidence of AE's related to clinically significant ECG/cardiac abnormalities

- Number/Incidence of AE's related to Heart Rate
 - Tachycardia (HR>100 bpm)
 - Bradycardia (HR < 50 bpm)
- Number/Incidence of AE's related to Blood Pressure
 - Hypotension
 - Hypertension
- Number/Incidence of AE's related to Liver Function
 - Liver function tests
- Number/Incidence of AE's related to Kidney Function
 - Renal function tests
- Number/Incidence of Mental and Psychotic AE's

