12.1. General Considerations

The proposed study is an open-label Phase I investigation intended to gather data on the safety, PK profile and preliminary efficacy of whole organic psilocybin mushrooms in patients suffering from PTSD.

The statistical analysis plan (SAP) will be finalized prior to database lock. The SAP will include a more technical and detailed description of the statistical analyses described in this section. This section is a summary of the planned statistical analyses of the most important, primary and secondary, endpoints.

Continuous variables will be summarized by descriptive statistics (number of cases, mean, and standard deviation, median, Q1, Q3, minimum, and maximum). Categorical variables will be summarized using counts of patients and percentages.

All analyses will be performed on patients who were administered the study drug (data on screen failure patients will be listed only).

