12.2. Sample Size

A sample size of up to 24 treated participants was selected because it is believed to provide sufficient data to determine whether psilocybin mushrooms are safe for this PTSD patient population.

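### Screening 30 at about 30% screen failure gives 21 treated, not 24, and Section 12.2 claims that up to 24 treated can settle whether the product is safe, which this design cannot do

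*Protocol*

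**What the plan says.** **Screening.** Protocol Section 7.1.1 says "Approximately 30 potential participants with PTSD may need to be screened to identify 24 participants" for the single dose. The next sentence adds "This figure assumes a screen failure rate of approximately 30" per cent. The same paragraph lets some treated participants who leave early be replaced: they "may be replaced at the discretion of the Investigator".

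**Number treated.** The Synopsis gives "24 treated participants". Section 12.2 makes it a ceiling: "A sample size of up to 24 treated participants was selected". The reason given is that this number is "believed to provide sufficient data to determine whether psilocybin mushrooms are safe for this PTSD patient population". No event rate, precision target or threshold accompanies it.

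**Analysis.** Safety is the primary objective (Section 3.1). Section 4.4.1 says "Primary endpoints will be assessed using descriptive statistics", and Section 12.1 says "All analyses will be performed on patients who were administered the study drug". There is no comparator, hypothesis test or success criterion for safety.

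**The concern.** Section 7.1.1 states a result and the assumption behind it in adjacent sentences, and the result does not follow from the assumption. A site that budgets for 30 screenings and meets the stated failure rate should expect to be three participants short of 24.

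Section 12.2 matters more because it concerns the primary objective. It is the protocol's only account of what 24 participants can show, and it says they can settle whether the product is safe. A reader of the final report could take that sentence as licence to call the product safe if no serious event is seen. The sample cannot support that conclusion for any but fairly common events.

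**Working it through.** **Part 1: screening**

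Inputs, from Section 7.1.1 and the Synopsis: screened about 30; screen-failure rate d about 0.30; target treated N = 24.

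1. Forward check of the plan's own figure: 30 × (1 − 0.30) = 21, which is 3 below 24.
2. Number needed: N/(1 − d) = 24/0.70 = 34.3, rounded up to 35. Check: 35 × 0.70 = 24.5.
3. Rate implied by 30 and 24: 1 − 24/30 = 0.20.
4. Effect of reading the rate loosely:

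| Screen-failure rate | Needed for 24 treated | Expected from 30 screened |
|---|---|---|
| 20% | 24/0.80 = 30 | 24 |
| 25% | 24/0.75 = 32 | 22.5 |
| 30% | 24/0.70 = 34.3, so 35 | 21 |
| 35% | 24/0.65 = 36.9, so 37 | 19.5 |

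Multiplying instead of dividing gives 24 × 1.30 = 31.2. That is close to 30 and may explain the slip, but it is not a valid screen-failure calculation. Replacing anyone already treated adds to the number to be screened.

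**Part 2: what 24 treated can show**

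Input: n = 24 treated (Synopsis, Section 12.2). Section 12.2 gives no calculation, so there is no figure to reproduce. The event rates below are illustrative, apart from the 7%, which Section 2.4 reports for tachycardia in a pooled analysis of healthy volunteers.

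1. Exact upper 95% limit when no event is seen:
   - one-sided: 1 − 0.05^(1/24) = 0.117, or 11.7%
   - two-sided: 1 − 0.025^(1/24) = 0.142, or 14.2%
2. With one event in 24, the exact two-sided 95% interval is 0.1% to 21.1%.
3. Probability that an event with true rate p is not seen at all, (1 − p)^24:

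| True rate p | Probability of no event in 24 |
|---|---|
| 1% | 79% |
| 2% | 62% |
| 5% | 29% |
| 7% | 18% |
| 10% | 8% |

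4. Because 24 is a ceiling, the limits widen if fewer are treated. With 21 treated and no event, they are 1 − 0.05^(1/21) = 13.3% one-sided and 1 − 0.025^(1/21) = 16.1% two-sided.

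**The case against.** The screening figure is a hedged forecast. Both numbers are approximate, screening numbers run to 099 (Section 5.2), nothing stops screening at 30, and no analysis uses the figure. All of this stands, and it limits the point to planning. It does not reconcile the two sentences: even at 25% failure the need is 32, and only 20% gives 30.

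On Section 12.2, the study is descriptive. It is meant to inform larger randomised trials (Section 2.2), has study-level pause criteria (Section 9.4) and a safety board (Section 11.1), and no planned analysis declares the product safe. For common effects 24 is informative: an event with a 10% true rate would be seen at least once with probability 92%. This stands too, and it is why the sample size itself is not criticised. It does not rescue the sentence, which claims more than a descriptive study can deliver.

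A reader might infer four stronger points, and the documents support none of them:

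- **That the trial has only a 16% chance of reaching 24.** That is the binomial probability that at least 24 of 30 pass at 70%. It applies only if screening stops at 30, and the protocol sets no such cap. Nor does it set an assurance level from which a screening target above 35 would follow.
- **That the 9-month duration is at risk.** No accrual rate or screening capacity is given, so the effect of about five more screenings cannot be judged.
- **That 24 is the wrong size.** No precision requirement is stated against which it fails.
- **That Section 12.3 is deficient because it names counts and percentages without confidence intervals.** The section lists its summaries as a minimum and the protocol leaves detailed methods to the SAP, which is not at hand.

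**Conclusion.** The point holds in two limited parts.

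Section 7.1.1 contradicts itself. At its stated rate the screening figure is about five too low (35 against 30), or, read the other way, the stated rate is ten percentage points too high for the figures of 30 and 24. The documents do not show which was intended. The consequence is a wrong recruitment budget, with no effect on bias or on any analysis.

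Section 12.2 attributes to the design a property it lacks. An event absent from all 24 participants could still have a true incidence of up to about 12% to 14%, depending on whether a one-sided or two-sided limit is used. This changes what may be concluded on the primary objective, so it is the weightier part.

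The limits assume that all 24 are treated and that events are independent between participants. Section 4.1 allows up to eight to be dosed together; positive correlation within a session would leave less information than these figures suggest.

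**What to change.** **Section 7.1.1.** Establish which number was meant. Either change the screening figure to approximately 35, or keep 30 and change the failure rate to approximately 20%. Add that the figure excludes any replacements.

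**Section 12.2.** Remove the claim that the sample can settle safety and put a precision statement in its place, for example:

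*With 24 participants treated and no occurrence of an event, the upper 95% confidence limit for its incidence is 11.7% one-sided (14.2% exact two-sided). An event with a true rate of 5% would be missed with probability 29%.*

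**Cost.** Two wording changes. If the 30% rate is right, about five more screenings need to be budgeted; if 20% is right, none. Design, eligibility, dosing and the number treated are unchanged. The stated safety claim becomes more modest.
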